		12.3.2 Statistical Analyses			
		12.3.3 Other Secondary Analyses			
		12.3.4 Sub study Analyses	53		
		12.3.5 Sample size calculation	54		
	12.4	Missing Data	54		
	12.5	Adverse Event Analysis	54		
	12.6	Interim Analysis	54		
13	ETHIC	CS/PROTECTION OF HUMAN SUBJECTS	55		
	13.1	Ethical Standard			
	13.2	Institutional Review Board	55		
	13.3	Informed Consent Process	55		

	13.4	Subject Confidentiality	55
		A HANDLING AND RECORD KEEPING	
15	PUBL	LICATION/DATA SHARING POLICY	59
16	LITEF	RATURE REFERENCES	60
APP	ENDIC	CES	62
		X A: SCHEDULE OF EVENTS	

LIST OF ABBREVIATIONS

AE Adverse Event/Adverse Experience

AMH Anti-Müllerian Hormone

BMI Body Mass Index

CD Cycle Day

CFR Code of Federal Regulations

CONSORT Consolidated Standards of Reporting Trials

CRF Case Report Form

DHEAS Dehydroepiandrosterone Sulfate
FDA Food and Drug Administration
FSH Follicle Stimulating Hormone

GCP Good Clinical Practice

HbgA1c Hemoglobin A1C

hCG Human Chorionic Gonadotropin

HIPAA Health Insurance Portability and Accountability Act

ICF Informed Consent Form

ICH International Conference on Harmonisation

IRB Institutional Review Board
IUP Intrauterine Pregnancy
LH Luteinizing Hormone

MedDRA[®] Medical Dictionary for Regulatory Activities

MOP Manual of Procedures

N Number (typically refers to subjects)

NIH National Institutes of Health

P4 Progesterone

PPCOS II Pregnancy in Polycystic Ovary Syndrome Study II

PI Principal Investigator
QA Quality Assurance
QC Quality Control

REDCap Research Electric Data Capture

SAE Serious Adverse Event/Serious Adverse Experience

SHBG Sex Hormone Binding Globulin
TSH Thyroid Stimulating Hormone

UIHC University of Iowa Hospitals and Clinics

WHO World Health Organization

PROTOCOL SUMMARY

Title: Randomized controlled trial of Combined Letrozole and Clomiphene

(CLC II) versus letrozole alone for women with anovulation

Précis: This is a multi-center, randomized controlled open-label clinical

trial of letrozole alone versus combination of letrozole and clomiphene citrate (CC) for up to 3 treatment cycles. Letrozole dosing will be increased in a stair-step fashion based on ovulation results. Participants will return for a mid-luteal ultrasound and progesterone lab to determine ovulatory status. Women will be randomized in a 1:1 ratio and the randomization scheme will be coordinated through the UIHC. Randomization will be stratified by site, age and BMI. The primary analysis will use an intent-to-treat approach to evaluate ovulatory rate in the

two treatment arms.

Objectives: To determine efficacy and safety of the combination letrozole and CC compared to letrozole alone in achieving ovulation in

infertile women with anovulation.

Primary Outcome: Ovulation will be the primary outcome determined by a mid-luteal progesterone level ≥ 3 and cumulative ovulation rate will be the primary efficacy parameter.

Secondary Outcome: Secondary efficacy parameters will include pregnancy rate (conception and clinical pregnancy), live birth rate, multiple gestation live birth rate, pregnancy loss rate (biochemical, miscarriage, ectopic) and time to pregnancy.

Side effect profile and complication rate will be monitored and reported.

Obstetric outcomes will include pregnancy complication rate, birth weight and sex, neonatal complication rate.

Ultrasound findings will be reported and compared between the two groups including: number of corpora lutea and endometrial thickness.

ClinicalTrials.gov Identifier

201906826

Population: 184 healthy women infertile women with polycystic ovary

syndrome or normogonadotropic normoestrogenic anovulation or oligo-ovulation, age \geq 18 to \leq 40. Additionally, the couple will

have no other major infertility factor.

Phase: IV

Number of Sites: 4 sites

University of Iowa Hospitals and Clinics Iowa City, IA with 2 ancillary sites

- Quad Cities Clinic, Davenport, IA
- Jordan Creek Clinic, Des Moines, IA

University of Wisconsin, Generations Clinic, Middleton, WI

Description Intervention:

of 184 women will be equally randomized to two different treatment arms at time of menses (spontaneous or induced with progestin withdrawal) or random start: A) letrozole 2.5 mg every day for 5 days (days 3-7 of cycle), or B) letrozole 2.5 mg and clomiphene citrate 50 mg every day for 5 days (days 3-7 of cycle), for a total of up to 3 treatment cycles.

Letrozole dose will be increased in subsequent cycles in both groups based on ovulatory response in stairstep fashion (details within protocol). Maximum letrozole dose will be 7.5 mg a day for 5 days.

Study Duration: 2 years

[figure not shown]
Subject **Participation Duration:**

Approximately 15 weeks of active participation time. Clinical chart abstraction and remote follow up will be continued until 6-8 weeks post-delivery in pregnant women.

Complete **Enrollment:**

Estimated Time to 20 months with 3 months follow up for final enrollees. 21 months by enrolling ~ 10 women per month across the 4 sites.

Schematic of Study Design:

Revised from PPCOS II Trial protocol study diagram

Detailed Schematic of Study Design:

Х

Obtain informed consent. Screen potential participants by inclusion and exclusion Screening Visit criteria; obtain history, physical exam. Pre-conception counseling. Progestin withdraw if indicated. Total: 184 Confirm negative pregnancy test, dispense meds, dispense and review Baseline journal log Visit (Cycle day 1-3, random start) Randomize Arm 1:92 Letrozole Arm 2:92 Letrozole + 50mg participants CC Participants to take Letrozole 2.5 + 1 pill study medication daily cycle days 3-5, Cycle day Participants to complete journal log and other assigned questionnaires 3-7 Repeat Perform midluteal assessments (transvaginal ultrasound, progesterone lab draw, cycles at Midluteal visit review journal log). adjusted Cylce day 18- 26 letrozole dosing as Progesterone < 3ng/mL needed Progesterone ≥ 3ng/mL Progesterone < 3ng/mL & no follicular up to 3 Participant awaits & follicular development development. Increase cycles menses and pregnancy Repeat progesterone in Letrozole dose by test at 2 wks) 10-14 days 2.5mg/day up to maximum dose of 7.5mg/day starting that day Progesterone ≥ 3ng/mL Increase Letrozole dose by 2.5mg/day up to maximum dose of 7.5mg/day starting with next Menses check in menses) Menses onset No menses: within two Menses onset. Confirm weeks - urine negative home pregnancy test pregnancy test prior to initiating new cycle Positive → serum Negative → Proceed with next cycle hCG confirmed: Move to Pregnancy follow up track

вазед оп NIDCR Clinical Trial (Interventional) Protocol Template v4.0 - 20140103

2.1 Background Information

Infertility in the US: The CDC National Survey of Family Growth (2011-2015) estimated that 7.3 million American women of reproductive age have used infertility services(1). Ovulatory disorders are the cause of approximately 30% of infertility(2). The most common ovulatory disorder, polycystic ovary syndrome (PCOS), comprises approximately 70% of anovulatory infertility cases(2). Based on these estimates, over 1.4 million American women have sought care for infertility related to PCOS. In this proposal, we focus on evaluating a novel cost- effective treatment strategy to improve fertility in women with PCOS. Current treatments for infertility and their limitations: Anovulatory disorders, specifically PCOS have been extensively studied, including significant research on oral ovulation induction agents by the NICHD Reproductive Medicine Network. This work has established letrozole as the first-line treatment for anovulation, due to superior delivery rates compared to clomiphene citrate (CC) (3). Although Letrozole is the preferred initial treatment, ovulation and delivery rates remain poor. For example, the PPCOS II trial demonstrated an ovulation rate over 5 treatment cycles of 61.7% with letrozole relative to 48.3%

with CC, with live birth rates of 27.5% and 19.1%, respectively (4). Thus, over 70% of women will not

achieve a live birth and will require more aggressive therapies.

More aggressive therapies pose greater risks, particularly to the children conceived. The second-line treatment for women who fail to conceive with oral agents is gonadotropin ovulation induction (3), which carries a dramatically higher risk of multiple gestation as compared to oral ovulation induction agents. Eijkemans *et al* found a 13.6% multiple gestation rate among pregnancies conceived with gonadotropins in anovulatory women, with a 4.5% rate of higher order multiples (5). In contrast, in the PPCOS II trial, twins comprised 3.4% of pregnancies conceived with letrozole and 7.4% of pregnancies conceived with CC, with no higher order multiple gestations (4). Women who fail gonadotropin ovulation induction regimens will often proceed to in vitro fertilization (IVF). Multiple birth rates with IVF, although dropping, remain significantly higher than those seen with letrozole or CC, with twins comprising 13.7-17% of live births (6). Furthermore, pregnancy complications such as preterm delivery and low birth weight are increased in singleton IVF pregnancies (7, 8).

Not only are risks increased with second- and third-line therapies, costs are also considerably higher. Gonadotropin ovulation induction has been estimated to cost an additional €3615 (\$4121) per live birth compared with CC (9). Costs of IVF are estimated to be more than *twenty times* the cost of ovulation induction medication (\$19,234 versus \$912) (10). These estimates do not account for the increased costs related to care for multiple gestations. More cost-effective therapies for ovulation induction in women with PCOS are urgently needed, due to the relatively poor outcomes of existing first line therapies, and the high expense and multiple gestation rates of second- and third-line therapies.

Mechanisms of drug action – potential for additive effect: CC is a non-steroidal selective estrogen receptor modulator that binds to the estrogen receptor in the hypothalamus. This central action affects the receptor recycling (11) and interferes with the normal feedback mechanism, resulting in increased

and prolonged FSH and LH secretion (12). These changes are more pronounced in the early follicular phase and are critical in initiating the development of follicles within the ovary. In a normo-ovulatory cycle, the rise in serum estrogen exerts a negative feedback in gonadotropin secretion.

Unlike CC, letrozole has a peripheral action whereby it blocks aromatase and the cytochrome P450 enzyme complex. This results in a peripheral hypo-estrogenic state, leading to increased FSH secretion. Letrozole also increases serum LH, androstenedione and testosterone levels (12). The rise in androgen levels increases follicular sensitivity to FSH by synergistic action with insulin-like growth factor (13-15) and FSH gene amplification (15, 16). The subsequent rise in serum estradiol provides a negative feedback on FSH, limiting multi-follicular recruitment and allowing endometrial proliferation (12).

[figure not shown]
CC has an antiestrogenic effect on endometrial development, which has not been demonstrated with letrozole. It is important to evaluate and confirm that by combining these two medications we do not see thinning of the endometrium demonstrated by ultrasound.

Herein we propose that the combination of letrozole and CC has an additive effect whereby CC decreases pituitary sensitivity to estrogen negative feedback while letrozole directly decreases serum estradiol, further promoting FSH secretion. We speculate that these alternate actions increase rates of ovulation and pregnancy in women with PCOS.

Preliminary Data

Addition of CC to letrozole improves ovulation rate: We investigated the impact of combining CC with letrozole as compared to letrozole monotherapy in 70 women with PCOS. We found that the combination of letrozole 2.5 mg and CC 50 mg nearly doubled the ovulation rate as compared to use of letrozole monotherapy (77% vs. 43%, P=0.007; rate ratio for ovulation (95% CI) 1.80 (1.18 to 2.75) (17). These results were achieved in a single treatment cycle, without any multiple gestations in our study cohort. In concordance with our findings, a prospective observational trial of combination letrozole and CC in patients who had previously failed CC and letrozole monotherapies found evidence of improved

ovulation, with development of a dominant follicle in 82.9% of cycles (18). While it is possible that the difference between the two arms in our preliminary study could be explained by a dosing effect, the ovulation rate in our combination treatment group was higher than the 61.7% cumulative ovulation rate across five cycles of letrozole monotherapy with increasing doses up to 7.5 mg (4). Our finding of a similar ovulatory rate within the letrozole monotherapy arm to that previously reported suggests an additive effect of the combination of these medications.

0.286

Addition of CC to letrozole does not negatively impact ultrasound parameters: Data from our pilot study suggest among the subgroup who ovulated, endometrial thickness and number of follicles were similar across treatment arms (Table 1). This is reassuring in that CC is not having a negative impact on

the endometrium and multi follicular development appears limited.

Both a commentary (19), and Fertility and Sterility Live Global Journal Club praised our pilot study, but emphasized the need for additional

•	•	Letrozole + CC Group n=25	p value
# of follicles > 15 mm	0.5 (0-1)	1 (0-1.5)	0.081
Largest follicle size (mm)	15.5 (10.0-18.3)	17.0 (13.5-19.5)	0.228

 8.6 ± 3.9

 7.4 ± 2.3

Table 1. Ultrasound characteristics among patients who ovulated

studies to evaluate escalating dosages, multiple cycles, live birth, and multiple gestation with this novel combination treatment. Given our promising initial data, the goal is to expand on our pilot and conduct a trial with escalating doses of letrozole across three cycles of either letrozole monotherapy or combination therapy in 184 women. This will provide not only additional data on ovulation rates but provide essential information on side effects, multiple gestation rate and live birth rate which will better situate us completing a multicenter study evaluating live birth rate.

Endometrial lining (mm)

Significance and Innovation

An improvement in the proportion of women with anovulatory infertility who conceive with oral ovulation induction agents is a public health imperative, as this increase can significantly reduce both the costs and complications of fertility treatments. We propose to study a **novel method** of oral ovulation induction with the combination of letrozole and CC. The mechanisms of ovulation induction differ when comparing letrozole (peripheral action at the ovary) and CC (central action in the hypothalamic-pituitary axis); therefore, it is reasonable to hypothesize that the two drugs combined have an additive effect. We have conducted the only randomized trial evaluating ovulation rates for this combination therapy compared to letrozole monotherapy. Our preliminary data demonstrate a nearly two-fold increase in ovulation rate with the combination of letrozole and CC, without evidence of an increase in the rate of multiple gestation (17). However, data comparing ovulation rates across multiple cycles with escalating Letrozole dosage is **critically needed** to plan a multi-center clinical trial to evaluate live birth rate.

2.2.2 Potential Benefits

Possible benefits to participants: The potential benefit to the participants is that they will receive a treatment (letrozole) that is known to improve ovulatory and pregnancy rates in women with infertility secondary to anovulation compared to no treatment at all or CC alone. The participant may receive a treatment (letrozole + CC) that may prove to be more effective than letrozole alone. Treatments may result in pregnancy although this cannot be guaranteed.

With ultrasound and hormone testing the participant may receive additional information regarding ovulation status.

Possible benefits to others: The study will provide important information on the treatment for women with infertility secondary to anovulation. This will provide knowledge on effective ovulation treatments for this patient population. The knowledge gained from this research may help discover an effective and safe way to achieve ovulation and pregnancy.

3 OBJECTIVES

3.1 Primary Research Hypothesis

The primary research hypothesis is that ovulation induction with the combination of letrozole and clomiphene citrate is more likely to result in ovulation (increased ovulation rate) than ovulation induction with letrozole alone in infertile women with anovulation (PCOS and/or normogonadtropic normoestrogenic anovulation or oligo-ovulation).

3.1.1 Primary Outcome Measure

The primary outcome measure is the occurrence of ovulation during the study period. Ovulation is defined as a mid-luteal progesterone level > 3 ng/mL. This will be tested 6-8 days following the patient reporting of an LH surge. If no LH surge is detected the lab will be drawn on cycle day 21-24. We will also analyze the ovulation rate of the follow up progesterone level.

We will utilize an intent-to-treat approach for the primary analysis of ovulation rate (utilizing the first progesterone level of each cycle) within the two treatment arms. If it is determined that timing of the initial progesterone level is inaccurate based on LH testing or patient symptoms, the progesterone test that is most clinically in line with accurate timing (6-8 days post LH surge) will be used. Ovulation rate will also be reported in those with a delayed response to treatment (needed repeat progesterone level due to anovulatory mid-luteal P4 level and follicle ≥ 14 mm). Patients will be analyzed according to the treatment group to which they are assigned, even if they did not receive the intended treatment or received only a portion of it. We will also perform a per protocol analysis to include only those patients who initiate treatment. Thus, those that are randomized but do not take the treatment due ineligibility will be excluded from the per protocol analysis. This per protocol analysis will provide data that is helpful to clinicians as it will include only those who initiated treatment.

3.2 Secondary Research Hypothesis and outcome measures

We will analyze secondary outcomes however due to sample size will not be able to power differences in pregnancy rate and live birth rate. Descriptive secondary outcomes will include positive pregnancy test, clinical pregnancy, and ongoing pregnancy. We will also evaluate number of corpora lutea determined by ultrasound, endometrial thickness and pattern by ultrasound. We will also monitor adverse events during treatment and side effect profile of both treatment arms.

We will evaluate pregnancy outcomes and report any fetal anomalies.

- 1. The combination treatment will result in higher live birth rate
 - a. Outcome measurement: live birth rate

- 2. The shortest time to pregnancy will be with the combination treatment.
 - a. Outcome measurement: time to pregnancy
- 3. Treatment with the combination will have a similar singleton pregnancy rate compared to treatment with letrozole.
 - a. Outcome measurement: Singleton pregnancy and singleton pregnancy rate; singleton pregnancy is defined as presence of single intrauterine gestational sac with a single fetal pole and observable heart motion. Multiple pregnancy rate will also be compared.
- 4. Treatment with the combination will have a similar pregnancy loss rate compared to treatment with letrozole.
 - Outcome measurements: Pregnancy loss (defined as spontaneous abortion occurring before 13 weeks gestation), biochemical (positive hCG test with spontaneously dropping hCG levels), ectopic pregnancy or pregnancy of unknown location
- 5. Side effect profile will be similar between both treatment groups.
 - a. Outcome measurements: # of days of reported side effects and acceptability of side effects.
- 6. Endometrial thickness and corpora lutea number will be similar between the two groups.
 - a. Outcome measurement: Endometrial thickness and corpora luteal number on CD21-23 transvaginal ultrasound or approximately 6-8 days following detection of LH surge. These outcomes will also be evaluated based on dosing.

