12.2 Statistical Analysis

All analyses will utilize the intention-to-treat (ITT) principle. All statistical tests of hypotheses will be two-sided. Baseline characteristics will be summarized by treatment arm. The primary outcome, cumulative ovulation, will be analyzed by comparing proportions utilizing a chi square test with significance set at 0.05. Dichotomous secondary outcomes will be analyzed in the same manner as the primary outcome. Two-sided t-tests will be used to compare endometrial lining thickness. Wilcoxon-Mann-Whitney tests will be used to compare number of corpora lutea. Time to pregnancy will be analyzed as a continuous variable using Kaplan-Meier survival analysis. Per-protocol analyses will be conducted to provide additional insight.

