12.5 Adverse Event Analysis

Adverse events will be categorized and frequency and percentage of patients experiencing adverse events and serious adverse events during the study period will be reported. Chi-square tests will be utilized to compare differences in proportion of total and categories of adverse events within each treatment arm.

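### Secondary hypotheses 3 to 6 predict similarity, but the plan offers only tests of difference and no criterion for calling the arms similar

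*Combined protocol and SAP*

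**What the plan says.** Section 3.2 lists six numbered secondary hypotheses. Items 1 and 2 predict an advantage for the combination. Items 3 to 6 predict no material difference:

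- Item 3: "Treatment with the combination will have a similar singleton pregnancy rate compared to treatment with letrozole". The multiple pregnancy rate is listed under this item as something to be compared.
- Item 4: "Treatment with the combination will have a similar pregnancy loss rate compared to treatment with letrozole".
- Item 5: "Side effect profile will be similar between both treatment groups", measured by days of side effects and their acceptability.
- Item 6: "Endometrial thickness and corpora lutea number will be similar between the two groups".

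The assigned analyses all look for a difference. Section 12.2: "Dichotomous secondary outcomes will be analyzed in the same manner as the primary outcome. Two-sided t-tests will be used to compare endometrial lining thickness". It adds a Wilcoxon-Mann-Whitney test for corpora lutea and sets 0.05, two-sided, for the primary chi-square test. Section 12.3.3 adds GEE models for differences. Section 12.5: "Chi-square tests will be utilized to compare differences in proportion of total and categories of adverse events within each treatment arm". No test is named for days of side effects. No margin, confidence-interval rule or other criterion for similarity appears.

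Section 12.3.5 gives power for item 6 among women who ovulate: 94% for 0.25 mm of endometrial thickness and 90% for 0.3 corpora lutea.

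**The concern.** A test of difference can reject equality but cannot establish similarity. If it is the only tool, the natural way to support items 3 to 6 is to point to p ≥ 0.05, which a small sample tends to give whatever the truth. For items 1 and 2 low power works against the hypothesis; for items 3 to 6 it works in its favour. Section 3.2 concedes low power only for pregnancy and live birth.

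These outcomes carry much of the safety half of the trial's objective. Section 2.2.1 says the multiple rate of the combination is unknown. Section 2.1 says of the endometrium: "It is important to evaluate and confirm that by combining these two medications we do not see thinning of the endometrium demonstrated by ultrasound". It also expects this trial's data on side effects and multiples to inform a later multicentre trial. An unsupported statement of similarity would pass into that design and into counselling.

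**Working it through.** **The plan's own figures first.** The 92 per arm (section 12.1.4) reproduces if ovulation is taken as 60% v 80% (the control rate is not stated): n = [1.96·√(2·0.7·0.3) + 0.842·√(0.24 + 0.16)]² / 0.2² = 81.2, so 82; 82/0.9 = 91.1, so 92. The comparisons in items 3 to 6 use this sample or subsets of it.

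The 94% for 0.25 mm does not reproduce. Assume 60% and 80% of 92 ovulate, about 55 v 74, so √(1/55 + 1/74) = 0.178. The endometrial SDs printed in sections 2.1 and 12.3.4 run from 2.2 to 3.9 mm. The standardised effect is 0.25/(2.2·0.178) = 0.64 down to 0.25/(3.9·0.178) = 0.36, giving t-test power of about 10% down to 6%. Power of 94% needs SD = 0.25/[(1.96 + 1.555)·0.178] = 0.40 mm.

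**Inputs for multiples.** From the plan, per pregnancy: letrozole 3.4%, CC 7.4%, gonadotropins 13.6% (sections 2.1 and 2.2.1). Assumed: conception in 20/25%, 25/33%, 30/40% or 40/50% of 92 women (letrozole/combination).

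**Method.** Sum the two binomial distributions over all outcomes for which Pearson X² = N(ad − bc)²/(product of the four margins) is below 3.84. The result is the chance of a non-significant test (a miss).

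| Pregnancies | 3.4% v 7.4% | 3.4% v 13.6% | Loss 25% v 40% (assumed) |
|---|---|---|---|
| 18 v 23 | 98% | 88% | 83% |
| 23 v 30 | 96% | 81% | 79% |
| 28 v 37 | 94% | 73% | 75% |
| 37 v 46 | 92% | 66% | 70% |

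Per randomised woman (92 v 92, rate = conception share × multiple rate), misses run from 95% down to 85% for the CC figure and from 78% down to 54% for the gonadotropin figure.

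**What significance would take at 23 v 30.**
- With 0/23 on letrozole, 5/30 is enough: X² = 53·(5·23)²/(23·30·5·48) = 4.23, p = 0.040.
- With 1/23, 7/30 is not enough (X² = 3.66, p = 0.056); 8/30 is (X² = 4.60, p = 0.032).
- At 3.4%, zero of 23 has probability 0.966²³ = 45%, and one of 23 has 37%.

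**Endometrium, 1 mm difference.** At 55 v 74 the standardised effect is 1/(2.2·0.178) = 2.55 down to 1/(3.9·0.178) = 1.44. Power is 72% down to 30%, so misses are 28–70%. The 95% CI half-width is about 0.8 to 1.4 mm.

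**Adverse-event categories, 92 v 92 (assumed rates).** 5% v 10% is missed 75% of the time and 10% v 20% is missed 52%.

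**What confidence intervals would show.** The Newcombe 95% CI for 2/30 minus 1/23 is −15 to +17 points. With no multiples in 30 pregnancies, the exact two-sided upper limit is 1 − 0.025^(1/30) = 11.6%. With none in 46 it is 1 − 0.025^(1/46) = 7.7%, still above 7.4%.

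**Could a formal margin be met for multiples?** With 3.4% in both arms, one-sided 0.025 and 80% power, n = 2·0.034·0.966·(1.96 + 0.842)²/margin². That is 447 pregnancies per arm for 3.4 points, 207 for 5 and 52 for 10.

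**The case against.** The strongest reply is that the plan nowhere says p ≥ 0.05 will be reported as similar. That is correct. A reader might infer that the trial is set to declare a doubled or quadrupled twin rate similar, but the documents do not support so firm a statement. On multiples the plan is cautious: its pilot saw none, yet it still calls the rate unknown and asks for more data. A reader might also infer that the plan hypothesises a similar multiple rate. It does not: item 3 applies the word to the singleton rate, and multiples are only compared. The two are close to complements per pregnancy, but the denominator is not stated.

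The pilot text does show how readily similarity can be concluded. Follicle counts above 15 mm with medians of 0.5 and 1 (p = 0.081) are described as similar, and of the endometrium it says "This is reassuring in that CC is not having a negative impact on" it. This is illustration only. The wording is hedged, the table is damaged in extraction, and section 12.3.4 shows a thicker endometrium on the combination (8.3 v 6.2 mm).

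The plan also has more than bare tests. Logistic, GEE and Cox models would yield effect estimates, section 12.3.1 compares the share of women who would decline treatment because of side effects, and the safety monitors see data on multiples. None of these says what result would count as similar.

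Section 12.3.5 might seem to cover item 6. It states power to detect a difference, not a margin, and its endometrial figure fails with the printed SDs.

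Finally, these are secondary outcomes, and margins for all of them would be excessive. That stands: for multiples, the smaller margins shown need several times the pregnancies expected.

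**Conclusion.** The point holds as a mismatch between hypothesis and analysis: items 3 to 6 claim similarity, and nothing in the plan can establish it. What does not hold is that the plan itself equates non-significance with similarity. That reading is only the one left open when no other rule is given.

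The size of the risk rests on assumed pregnancy and ovulator counts, assumed loss and adverse-event rates, and SDs that were not labelled mid-luteal (two come from cycle days 12–14). The conclusion for multiples is stable across the range: at the CC rate a miss is 85–98% likely on either denominator, and at the gonadotropin rate it stays above one half throughout. For the endometrium it depends on the SD. No calculation was made for the singleton rate itself. The plan should be changed before analysis.

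**What to change.** 1. In sections 12.2 and 12.5, state that a non-significant test will not be read as similarity or safety. Base conclusions for items 3 to 6 and adverse events on the difference (combination minus letrozole) with its two-sided 95% CI, using a score (Newcombe) interval for proportions. Call the result inconclusive when the interval includes clinically relevant harm.
2. Reword items 3 to 6 of section 3.2 so that each outcome is estimated with a 95% CI. State the denominator for singleton and multiple rates, and name the analysis for days of side effects.
3. Report the exact upper 95% limit for the multiple rate in the combination arm, and acknowledge in advance that the trial is unlikely to exclude 7.4%.
4. Formal margins are optional, and worth setting only where the sample can meet them, for example endometrial thickness. Recheck the 0.25 mm statement in section 12.3.5 and print its SD.

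The cost is a few sentences, with no new patients or data. The downside is that multiples and loss will probably be reported as inconclusive.
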